## **9. Quality Assurance, Data Handling, Publication Policy and Finance**

The Principal Investigator will take overall responsibility for the internal monitoring of all CRFs, taking care to ensure that entries are complete and legible and to otherwise ensure compliance to the protocol, and to ICH GCP. The Investigator will permit representatives of the regulatory authorities to inspect facilities and records relevant to this study.

The Investigator will be responsible for preparing the final study report. All results generated in this study may be submitted for publication or presentation.

The study has been funded by the Medical Research Council.

## **10. Data Management**

Case report forms (CRFs) will be developed by the Data Management team at the Wolfson Centre for Personalised Medicine along with the lead Investigator, the Trial statistician and the lead research nurse. A bespoke database will be produced using specific clinical trials database design software. CRF data entered into the database designed for this study will be centrally monitored by the data management team, to ensure that data collected is consistent in accordance to the study protocol. The database used for this study will include validation features that notify the user to when certain validations are violated. If any irregularities are identified via automated validation or central monitoring, a discrepancy will be raised within the database and a notification will appear in the users login screen to action. A complete log of discrepancies and data amendments is automatically generated, including the date of each change, the reason for the change and the user who action the change, thus providing a complete audit trail. Additional site training will be carried out if recurring problems are noted with data from a certain site, such as consistently incorrect or incomplete data, a backlog of unresolved discrepancies, or unacceptable time delays in submitting CRFs.

## **11. Data Monitoring**

A generic study monitor is employed by the department. Through a variety of processes the monitor will ensure; that the study meets ICH-GCP compliance, that all staff working on the study are trained competent and authorised to do so, that study data integrity is maintained, that patient safety and data protection are not compromised, that all documents and approvals are in place prior to and during the period of the study etc

Protocol V17 07.02.2023

## 12. Appendices

### 12.1 Appendix 1: Abbreviations

ADR:	Adverse Drug Reaction
CRF:	Case Report Form
DNA:	Deoxyribonucleic acid
GPRD:	General Practitioner Research database
MHRA:	Medicines for Health Regulatory Authority
PIL:	Patient Information Leaflet
PMH:	Patient Medical History
RNA:	Ribonucleic acid
YCC:	Yellow Card Centre

Protocol V17 07.02.2023

## 12.2 Appendix 2: Patient Visit Schedule for Drug Class NOS studies

**Visit 1: Patient Recruitment (Identification of patients on active drug treatment either with or without evidence of ADR to drug).**

1. Consent	Written and verbal consent for inclusion into study
2. Blood sampling	Blood sample (up to 500mL) collected into a lithium/heparin / EDTA vacuette
3. Initial assessment	PMH/admission details  Current medications (including herbal and over the counter medications)  Alcohol/smoking/recreational drug use  Height/weight/ethnicity

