## **5. Sampling and Data Collection**

### **5.1 Blood Sampling**

Hypersensitive patients and patients that can tolerate the drug of interest without hypersensitivity reactions will also be recruited; the samples provided by this control patient cohort will act as experimental controls.

The adult patients will be asked initially to provide 50mL venous blood sample from which we will isolate the plasma and mononuclear cells using density gradient centrifugation. The volume of blood from paediatric patients will be less than this, and will conform to EMA guidelines and will not exceed 1% of total body circulating volume at a single sample, or 3% in a 4 week period. The current laboratory techniques require a minimum volume of blood for a successful sample analysis, although this will decrease as the technologies evolve during the study period. Children and young people whose weight requires a sample less than the minimum volume required for successful analysis will not be recruited. The minimum volume required will be determined by regular consultation with the laboratory team during the study. When biological samples including peripheral blood mononuclear cells (from hypersensitive and tolerant patients) are imported from collaborators under their own protocols and ethical approval, cells will be cryopreserved at the collaborating site and transported in a cryogenic environment (eg. dry ice, liquid nitrogen). The cells will be defrosted in Liverpool and used in the same way as samples collected from other sources in the experiments described below.

Protocol V17 07.02.2023

Plasma will be used for bioanalysis; DNA will be used for HLA typing and profiling drug specific changes in gene expression. Cells will be used for:

- (a) Standard lymphocyte proliferation assays and an assay that incorporates a metabolising system.
- (b) Generation and characterisation of drug specific T cell clones.
- (c) Generation of immortalised Epstein-barr virus transformed B cell lines to be used an autologous population of antigen presenting cells.

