Storage in liquid nitrogen to restimulate responding T cell lines and clones as and when required. Adult patients that produce the most vigorous response in the lymphocyte transformation test (LTT) may be asked to donate further blood samples; the patients that are re-called will be asked to donate up to 60mL of venous blood. We believe it is important to make these patients aware of the LTT result to their medication(s), so that severe reactions can potentially be avoided in the future. Paediatric patients will be assessed on a case by case basis. Any further requests for blood samples will be guided by the EMA guidelines (and the wishes of the patient/family) but will not exceed 3% total circulating volume in a 4-week period (approx. 2.4ml/kg).

For patients taking oncological immunotherapies, those displaying hypersensitivity and those tolerant to the drug will both be recruited. The samples provided by this control patient cohort who do not display hypersensitivity will act as experimental controls. Patients receiving PD-1 inhibitor monotherapy or in combination with a CTLA-4 will be recruited into the study.

The adult patients will be asked to donate up to 50mL venous blood samples (schedule seen in 5.1.2.2) from which we will isolate the plasma and mononuclear cells using density gradient centrifugation. This arm of the study will not be recruiting paediatric patients

Samples will be analysed as follows:

- a. Whole blood (including PBMCs post isolation) samples will be analysed for the presence of T-cell populations and subpopulations, cell surface and intracellular immune markers using Mass Cytometry using Time of Flight technology (CyTOF) and/or Flow cytometry
- b. Whole blood samples and PBMCs (isolated from whole blood) will be analysed for the presence of cytokines using CyTOF
- c. Plasma will be used for cytokine analysis using cytokine arrays and ELISA techniques
- d. Serum will be used to determine the presence of autoantibodies utilising protein array technology and ELISA techniques
- e. Transcriptomic analysis
- f. HLA typing

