### Visit 2: Patient Recall

1. Consent	Verbal consent for continuation in the study
2. Blood sampling	1 blood sample (Up to 60mL) collected into a lithium/heparin vacuette

For each adult case or control, up to a total of 180mL of blood will be collected per year for a maximum of 3 years. For paediatric patients, the minimal blood volume possible will be used, and will not exceed amount stated in EMA guidelines.

If, after 3 years of blood donation, the data generated from a particular adult patient warrants further investigation, we will approach the subject to re-consent for further blood donations to continue as specified above (a maximum of 180mL per year).

Protocol V17 07.02.2023

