The sampling schedule may be modified in terms of the number of visits on clinical, patient choice or geographical grounds as not all patients will be able to attend for all visits. If patients experience toxicity during time on the cohort study a further blood sample will be taken at that point. If patients experience toxicity after the conclusion of the sampling schedule a patient will be offered the opportunity of donating an additional sample of blood or enrolment on to the case-control study.

Microbiome samples may be taken throughout enrolment on the study

We will not request that subjects donate more than 475mL of blood in a period of 16 weeks. This is the blood donation volume and rate adopted by the National Blood Service for England and Wales ([www.blood.co.uk](http://www.blood.co.uk)) and is thus a well recognised national standard.

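### Appendix 2 permits up to 500 mL of blood at Visit 1: ten times the Section 5.1 volume and 2.8 times the yearly ceiling in the same appendix

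*Protocol*

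**What the plan says.** Section 5.1.2.1 of the protocol sends the reader to Appendix 2 (12.2) for the Drug Class NOS visit schedule. The Visit 1 row there reads "Blood sample (up to 500mL) collected into a lithium/heparin / EDTA vacuette".

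Three other statements bear on the same adults:

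- Section 5.1, on the first draw: "The adult patients will be asked initially to provide 50mL venous blood sample".
- Appendix 2, below the Visit 2 table: "For each adult case or control, up to a total of 180mL of blood will be collected per year for a maximum of 3 years". The same yearly maximum is repeated for adults who re-consent after three years.
- The recall draw is given twice, with the same volume. Appendix 2, Visit 2 has "1 blood sample (Up to 60mL) collected into a lithium/heparin vacuette", and Section 5.1 says that "the patients that are re-called will be asked to donate up to 60mL of venous blood".

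For comparison only, the oncology schedules in Appendix 3 carry their own limit: "We will not request that subjects donate more than 475mL of blood in a period of 16 weeks". The protocol does not apply that limit to the Drug Class NOS participants.

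**The concern.** The Visit 1 volume cannot be used to its limit without breaking both Section 5.1 and the yearly ceiling printed just below it. The protocol gives no rule for which figure prevails and no reason for a draw of this size.

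What is at stake is participant safety, not inference. Appendix 2 is operational text. Recruitment is local and national and comes from many sources, so sites cannot be assumed to share the coordinating team's understanding of what was meant. Cases may be in hospital with an acute drug reaction, and the adult eligibility criteria in Section 4.1.1 set no weight or haemoglobin threshold; suitability is left to the investigator's opinion. The written volume limits therefore carry much of the protection. Section 6 assesses risk on the basis of ordinary venepuncture, and Section 8 plans no adverse event reporting beyond a CRF note of venepuncture problems. Neither contemplates a donation-sized draw. A monitor checking Visit 1 against the schedule could pass any volume up to 500 mL.

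**Working it through.** **Inputs (adults, Drug Class NOS)**

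| Quantity | Value | Source |
|---|---|---|
| Visit 1 draw | up to 500 mL | Appendix 2, Visit 1 |
| Initial draw | 50 mL | Section 5.1 |
| Recall draw | up to 60 mL | Section 5.1; Appendix 2, Visit 2 |
| Yearly ceiling | 180 mL | Appendix 2, after Visit 2 |
| Oncology limit (comparison only) | 475 mL in 16 weeks | Appendix 3 |

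**Step 1. Does the Visit 1 figure fit the protocol's own limits?**

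- Against Section 5.1: 500 / 50 = 10.
- Against the yearly ceiling: 500 / 180 = 2.78, so about 2.8 times, an excess of 500 − 180 = 320 mL from a single visit.
- Visit 1 plus one recall: 500 + 60 = 560 mL, and 560 / 180 = 3.1.
- Against the oncology limit: 500 / 475 = 1.05. Even the more generous limit used elsewhere in the protocol would be exceeded in one sitting.

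**Step 2. Which figure is out of line?** Replace 500 mL with the Section 5.1 volume:

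- One recall: 50 + 60 = 110 mL.
- Two recalls: 50 + 60 + 60 = 170 mL.

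Both are within 180 mL. The recall volume is the same in both places where it appears. The initial volume, the recall volume and the ceiling form a consistent set, and only the Visit 1 entry falls outside it.

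**Step 3. What Visit 1 volume would the ceiling bear?**

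- No recall that year: at most 180 mL.
- One recall at full volume: 180 − 60 = 120 mL.
- Two recalls at full volume: 180 − 120 = 60 mL.

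The Section 5.1 figure of 50 mL satisfies all three. The Appendix 2 figure satisfies none.

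**The case against.** The strongest reply is that this is one stray digit, and that the same appendix already contains it. The entry is an upper bound, not an instruction. A site that reads on meets the 180 mL ceiling, and anyone who also reads Section 5.1 meets 50 mL. A trained professional filling vacuettes would probably query 500 mL. Reaching 560 mL would require ignoring both statements. Children are protected separately, by limits of 1% of circulating volume per draw and 3% over four weeks in Section 5.1 and by the reference to EMA guidance in Appendix 2. The 475 mL limit belongs to the oncology schedules and is not breached as a rule here. No endpoint, sample size or analysis is affected. Participant information sheets and any sampling manual are not at hand and may carry the right figure.

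Most of this stands. The probable cause is a typing error, the concern is confined to adults, the oncology limit is only a benchmark, and the practical chance of harm is low. What does not follow is that the entry can be left. A ceiling that contradicts the row above it is part of the defect, because a site must notice the conflict and choose between the two figures without guidance. A tenfold discrepancy in an approved limit on what may be taken from a participant should not depend on sites noticing it.

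**Conclusion.** The concern holds. The Visit 1 limit in Appendix 2 is wrong as written: 10 times the Section 5.1 volume, 2.8 times the yearly ceiling in the same appendix, and 3.1 times that ceiling once a single full recall draw is added. It is a contradiction in a participant-safety limit, not an unconditional permission to draw 500 mL.

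The ratios rest only on figures printed in the protocol. That 50 mL was intended is an inference: it matches Section 5.1 and leaves room for two full recalls in a year. The contradiction does not depend on that inference, since any Visit 1 draw above 180 mL breaks the ceiling on its own. Because the figure governs what is done to participants and costs almost nothing to correct, it must be fixed, although harm is unlikely.

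**What to change.** Amend the Visit 1 blood-sampling row of Appendix 2 so that it agrees with Section 5.1 and so that Visit 1 plus recall draws cannot exceed 180 mL in a year. An entry of 50 mL does this. The sponsor should confirm the intended volume; if a larger one is really wanted, Section 5.1 and the yearly ceiling have to be changed and justified with it. It would help to mark the row as applying to adults and to point to the paediatric limits.

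Until the amendment is in force, write to all sites telling them not to use the present Visit 1 figure and to keep to Section 5.1 and the yearly ceiling.

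The cost is a one-line amendment and a site notice. Nothing in the design, the assays or the analysis changes.

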### Visit 2: Patient Recall

1. Consent	Verbal consent for continuation in the study
2. Blood sampling	1 blood sample (Up to 60mL) collected into a lithium/heparin vacuette

For each adult case or control, up to a total of 180mL of blood will be collected per year for a maximum of 3 years. For paediatric patients, the minimal blood volume possible will be used, and will not exceed amount stated in EMA guidelines.

If, after 3 years of blood donation, the data generated from a particular adult patient warrants further investigation, we will approach the subject to re-consent for further blood donations to continue as specified above (a maximum of 180mL per year).

Protocol V17 07.02.2023

### 12.3 Appendix 3: Patient Visit Schedule for Oncological Immunotherapy studies

As per the pharmacokinetic subsection please note that on the basis of the initial assessments, participant availability and flexibility, we may change the sampling schedule but we will keep the total number of samples per patient constant.

#### ***Patient Visit Schedule for the Case-Control Study***

A flexible sampling window of +/- 7 days will be allowed in both case and control groups.

#### **Cases**

Day 0: Patient Recruitment (Identification of patients who have had an irAE to an immunotherapy CPI or non-hypersensitive control patient)

Patients will ideally be recruited and a blood sample taken prior to the introduction of initial steroid therapy; however patients can still be recruited if it is within 7 days of commencement of steroid therapy.

Visit 1: Day of recruitment (Day 0)

1. Consent	Written and verbal consent for inclusion into the study
2. Blood sampling	50mls of blood collected into lithium/heparin (or CPT), EDTA and serum tubes (+/- PAXgene).  Optional Stool Sample
3. Initial Assessment	Malignant site and current disease status  Therapeutic history  PMH (particularly of autoimmune disease)  FH (particularly of autoimmune disease)  Current medications (including herbal and over the counter medications)  Alcohol/smoking/ recreational drug use  Height/weight/ethnicity

Subsequent Sampling (All Organ Sites) – if antibody analysis is not needed at each point then can reduce the amount of blood needed at each point.

Week 0 (Day 1)	Blood Sampling	40mls Blood
Week 1 (~Day 7)	Blood Sampling	40mls Blood

Protocol V17 07.02.2023

Week 2 (~Day 14)	Blood Sampling	40mls Blood
Week 3 (~Day 21)	Blood Sampling	40mls Blood
Week 4 (~Day 28)	Blood Sampling	40mls Blood
Point of resolution of symptoms or biochemical disturbance (as applicable) 	Blood Sampling	40mls Blood
Point of recurrence (if applicable)	Blood Sampling	40mls Blood
Week 8 (~Day 56)	Blood Sampling	40mls Blood

Resolution of symptoms to be used in the case of colitis and dermatitis and biochemical restoration to be used in the case of hepatitis and thyroid disturbance.

Patients recruited with biochemical thyroid dysfunction or hepatitis will have an additional sample taken if/when their biochemical profiles begin to normalise

The sampling schedule may be modified in terms of the number of visits on clinical, patient choice or geographical grounds as not all patients will be able to attend for all visits. On occasion a single sample at the point of toxicity will be taken if no further samples are possible on clinical grounds. Additionally if a patient experiences an additional toxicity during enrolment an additional blood sample may be taken.

Microbiome samples may be taken throughout enrolment

### **Controls**

A single sample will be taken at a matched time point to cases and subsequent samples will be taken at the start of month 4 (~day 84) following the first sample (even if CPI has been discontinued on non-toxicity ground eg disease progression). Patients will have 40mls of blood taken at each visit and may have microbiome samples taken alongside. If control patients wish to contribute further to the study and give further blood samples at different durations of therapy for further matching this will be permitted.

We will not request that subjects donate more than 475mL of blood in a period of 16 weeks. This is the blood donation volume and rate adopted by the National Blood Service for England and Wales ([www.blood.co.uk](http://www.blood.co.uk)) and is thus a well recognised national standard.

### ***Patient Visit Schedule for Cohort study***

Baseline Visit: Patient Recruitment (Identification of patients due to commence PD-1 inhibitor monotherapy or PD-1/CTLA-4 combination therapy). A flexible sampling window of +/- 14 days will be allowed as long as it remains prior to the commencement of therapy.

Protocol V17 07.02.2023

1. Consent	Written and verbal consent for inclusion into the study
2. Blood Sampling	50 mls of blood collected into lithium/heparin (or CPT) / EDTA /serum tubes (+/- PAXgene). Optional Stool Sample
3. Initial assessment	
Malignant site and current disease status
 
Therapeutic history
 
PMH (particularly of autoimmune disease)
 
FH (particularly of autoimmune disease)
 
Current medications (including herbal and over the counter medications)
 
Alcohol/smoking/ recreational drug use
 
Height/weight/ethnicity

Visit 1: Pretreatment sample within 0-2 days of commencing treatment

1. Consent	Verbal consent for continuation of the study
2. Blood Sampling	50mls of blood collected into lithium/heparin (or CPT), EDTA and serum tubes (+/- PAXgene).
3. Current circumstances	Determine changes to current state of health and medication

Visit 2: Week 0 (Day 1) – the day of initial CPI treatment

4. Consent	Verbal consent for continuation of the study
5. Blood Sampling	40mls of blood collected into lithium/heparin (or CPT), EDTA and serum tubes (+/- PAXgene).
6. Current circumstances	Determine changes to current state of health and medication

Subsequent Visits

Week 1 (~Day 7) Visit 3	Blood sampling	40mls of blood
Week 2 (~Day 14) Visit 4	Blood sampling	40mls of blood

Protocol V17 07.02.2023

Week 3 (~Day 21) Visit 5	Blood Sampling	40mls of blood
Week 4 (~Day 28) Visit 6	Blood Sampling	40mls of blood
Week 8 (~Day 56) (Start of treatment month 3) Visit 7	Blood Sampling	40mls of blood
Week 12 (~Day 84) (Start of month 4) Visit 8	Blood sampling	40mls of blood

Patients will have their consent to continue in the study and their current status regarding medical circumstances and medications verbally confirmed at the beginning of each visit.

The sampling schedule may be modified in terms of the number of visits on clinical, patient choice or geographical grounds as not all patients will be able to attend for all visits. If patients experience toxicity during time on the cohort study a further blood sample will be taken at that point. If patients experience toxicity after the conclusion of the sampling schedule a patient will be offered the opportunity of donating an additional sample of blood or enrolment on to the case-control study.

Microbiome samples may be taken throughout enrolment on the study

We will not request that subjects donate more than 475mL of blood in a period of 16 weeks. This is the blood donation volume and rate adopted by the National Blood Service for England and Wales ([www.blood.co.uk](http://www.blood.co.uk)) and is thus a well recognised national standard.

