#### **4.2.5 *Co-enrolment Guidelines***

Patients registered for the Hypersensitivity study are not restricted to entry onto any other clinical trial, study or research project as this study consists of blood sampling. However information regarding any trial participation will be collected on the follow-up CRF forms.

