A paired blood sample (50mls) and urine sample (25mls) will be taken alongside the tissue sample. The urine will be frozen and/or freeze dried. Analysis utilising cytometry techniques, other forms of cellular/ cytokine analysis, transcriptomics and additional protein or gene analysis will be undertaken to characterise hepatotoxicity including potential pathological mechanisms. Alongside liver biopsy and blood/urine sampling a liver stiffness assessment will be undertaken. This is a non-invasive ultrasound based modality which carries no procedural risk.

If patients do not wish to give a liver biopsy then a single blood +/- urine +/- stiffness test can also be taken as part of this study arm.

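### Cohort patients who transfer to the case-control study soon after day 84 can exceed the protocol's limit of 475 mL of blood in 16 weeks, and the protocol does not say how the limit would then be kept

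*Protocol*

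**What the plan says.** Appendix 3 gives the limit twice, after the case-control schedule and after the cohort schedule: "We will not request that subjects donate more than 475mL of blood in a period of 16 weeks".

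The same appendix sets these draws:
- **Cases:** 50 mL on day 0, then 40 mL at each of eight points (day 1, weeks 1, 2, 3, 4 and 8, resolution, and recurrence if it occurs).
- **Cohort:** 50 mL at baseline, 50 mL just before treatment, then 40 mL at each of seven visits (day 1, weeks 1, 2, 3, 4, 8 and 12).

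It then adds samples without stating a volume. For cases: "Patients recruited with biochemical thyroid dysfunction or hepatitis will have an additional sample taken if/when their biochemical profiles begin to normalise", and "Additionally if a patient experiences an additional toxicity during enrolment an additional blood sample may be taken". Cohort patients give a further sample at any toxicity during the series. For toxicity after the series ends, "a patient will be offered the opportunity of donating an additional sample of blood or enrolment on to the case-control study".

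The tissue sections have their own blood draws. For liver, section 5.3.4 says "A paired blood sample (50mls) and urine sample (25mls) will be taken alongside the tissue sample". Sections 5.3.1 (colon) and 5.3.3 (thyroid) also specify 50 mL, and the skin sections up to 50 mL. None of them mentions the limit.

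Two provisions bear on how the limit could be kept. The opening of Appendix 3 allows the schedule to change but holds the number of samples per patient constant. The case and cohort schedules allow the number of visits to change on clinical, patient-choice or geographical grounds. Blood volume is not named as a ground.

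**The concern.** This is the only cumulative blood limit in the protocol for adult oncology participants. The others belong to Drug Class NOS adults (180 mL a year), to children, and to the pharmacokinetic sub-study. A cohort patient who becomes a case starts a second serial schedule when most of the first still lies inside the 16-week window. The two schedules appear to have been checked against the limit separately, not in sequence.

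At stake is whether a commitment made to patients with active toxicity can be kept. A site that notices the conflict has a limit, a schedule and a rule holding the number of samples constant, with no order of precedence among them.

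**Working it through.** **Inputs.** Volumes and days are those of Appendix 3. The window is 16 × 7 = 112 days. Assumptions: the cohort pre-treatment draw is on day 0; baseline falls between day −14 and day −2; case day 0 is the day of transfer; add-on samples without a stated volume are 40 to 50 mL.

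**Each schedule alone**
- Case: 50 + 8 × 40 = 370 mL. With the normalisation sample and one additional-toxicity sample: 370 + 2 × 40 = 450 mL, or 370 + 2 × 50 = 470 mL.
- Cohort: 50 + 50 + 7 × 40 = 380 mL. With one toxicity sample: 420 to 430 mL.

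All are below 475 mL.

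**Transfer on day 85, fixed-day draws only.** Case draws fall on days 85 (50 mL), 86, 92, 99, 106, 113 and 141 (40 mL each).
- Baseline on day −14: the heaviest window is days 0 to 111. Cohort draws in it: 50 + 7 × 40 = 330 mL. Case draws on days 85, 86, 92, 99 and 106: 50 + 4 × 40 = 210 mL. Total 330 + 210 = 540 mL.
- Baseline on day −2: the heaviest window is days −2 to 109. All cohort draws, 380 mL, plus the same 210 mL, give 590 mL.

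The excess is 540 − 475 = 65 mL to 590 − 475 = 115 mL. Put another way, 475 − 330 = 145 mL or 475 − 380 = 95 mL remains for case draws scheduled at 210 mL.

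**How long the conflict lasts.** Largest total in any 112 days, fixed-day draws only:

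| Day of transfer | Baseline day −14 | Baseline day −2 |
|---|---|---|
| 85 | 540 mL | 590 mL |
| 91 | 500 mL | 550 mL |
| 97 | 500 mL | 510 mL |
| 98 | 460 mL | 510 mL |
| 102 | 460 mL | 510 mL |
| 103 | 460 mL | 470 mL |

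The last transfer day above the limit is therefore 97 to 102. One toxicity sample during the cohort series raises the day-85 total to 580 to 640 mL and moves the last day to 104 to 109. With every conditional case sample placed inside the eight-week case schedule, the last day is about 139.

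**Other combinations, if all draws fall within 16 weeks**
- Hepatitis or thyroid case with resolution, recurrence, normalisation, one further toxicity (40 mL each) and a separate 50 mL tissue draw: 450 + 50 = 500 mL.
- Cohort plus the prospective skin arm (section 5.3.2.2, up to 50 mL then 40 mL): 380 + 50 + 40 = 470 mL. A toxicity sample makes it 510 to 520 mL. Appendix 11 lists 40 mL at both skin visits, which would give 500 to 510 mL.

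**The case against.** The strongest reply is that no overrun is required. The limit is worded per subject, so it can already be read as binding a transferring patient. Transfer is optional, and a single extra sample is the stated alternative. Visits may be reduced, volume may be cut when antibody analysis is not needed, section 5.1 words oncology draws as up to 50 mL, and one sample at toxicity is acceptable on clinical grounds. The transfer conflict also assumes full attendance in both series. All of this stands, and it confines the point to a timing gap.

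The 500 mL case is weaker than the transfer example. It stacks every conditional sample and a tissue draw that the protocol does not say is additional to the scheduled one. Section 5.3.3 also calls these endocrinopathies irreversible, which makes early normalisation and resolution less likely in thyroid cases.

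What does not fall away is precedence. The permission to change visits sits beside a statement that the number of samples stays constant, and neither is tied to the volume limit.

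A reader might also infer three stronger things:
- **Blood taken in other studies must be counted.** Section 4.2.5 leaves participants "not restricted to entry onto any other clinical trial, study or research project as this study consists of blood sampling", but the limit concerns what this study requests, and other trial participation is recorded on the CRF.
- **Nobody could see the limit being reached.** Appendix 7 lists no blood total, but it is a list of clinical data. Section 5.4 describes bar-coded sample tracking and section 11 a study monitor.
- **Late samples would be lost selectively in the sickest patients.** No passage says which draws a site would drop.

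**Conclusion.** The point holds in a limited form. The oncology schedules do not in themselves exceed 475 mL, and a reader who infers that they do is mistaken: the totals are 370 and 380 mL, and at most 470 and 430 mL with one of each Appendix 3 add-on.

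The offered transfer can exceed the limit on fixed-day draws alone, by 65 to 115 mL at day 85, for transfer up to about day 97 to 102. That result uses only stated volumes. It rests on full attendance, on the assumed baseline dates, and on the case schedule starting on the day of transfer. The tissue and skin-arm combinations can also exceed the limit, but they depend on assumed volumes and on several conditional samples coinciding.

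The defect is that the transfer offer, the add-on samples, the paired tissue draws and the constant-number clause have not been reconciled with the limit. How many patients this would affect cannot be estimated from the protocol.

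**What to change.** - Reconcile the opening of Appendix 3, its case and cohort schedules, and sections 5.3.1 to 5.3.4 with the 475 mL limit. Make clear which provision yields when they conflict. How this is done is for the sponsor to decide.
- State that the limit applies per participant across all arms of this study, including draws made before transfer from the cohort.
- Give the volumes of the normalisation, additional-toxicity and cohort-toxicity samples, and say whether a paired tissue sample is additional to the draw scheduled at that time.
- Keep a running total of research blood for each participant.

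The cost is protocol wording and one recorded item. The small downside is that some draws may be reduced or not taken in a minority of patients.
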